# 1.3.4. Urine samples

Participants collected the first urine sample of the morning in a sterile container given to them previously. Once the sample was collected, participants stored it under refrigeration (for no more than 24-48h) until it was delivered to the researchers. Samples were stored at -20°C until use.

# 1.3.4.1 Nitrates and nitrites analysis

Urine samples were used to analyse nitrate and nitrite content. The samples were diluted 1:10, then 1 ml of Carrez I ( $K_4$ [Fe(CN6)·3H20) and 1 ml of Carrez II (ZnSO4 x 7H2O) were added and stirred for 30 minutes at room temperature. After this time, the mixture was filtered through a 150 mm Ø filter paper. Finally, the samples were analysed in a SmartChem.

#### 1.4. Statistical analysis

Data analysed were expressed as mean  $\pm$  standard deviation (SD). Student's t-test was used to analyse significant differences over time (baseline and final). To analyse the differences between groups in the evolution of the different variables, an analysis of variance (ANOVA) was performed for repeated measures, with time (baseline and final) as the within-subject factor, and the product consumed (Control and Intervention) as the between-subject factor. Tukey's test was carried out for post hoc analysis. Cross-tabulation and chi-square tests were conducted to determine the perception of respondents on food additives based on demographic data.

Data processing and statistical analysis were performed using SPSS version 28.0 (IMB Corp., Armonk, NY, USA) with a significant level of  $p \le 0.05$ .

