#### 1.1. Trial Design

This study consisted of a double-blind, randomised, controlled, unicentric trial with two parallel arms depending on the cooked meat product consumed (control and reformulated), with a duration of 5 weeks. The study was approved, according to the Declaration of Helsinki, by the Bioethics Committee of the University of Murcia (UMU) with code 550/2023. The research took place at the Department of Nutrition and Bromatology of the Faculty of Veterinary Medicine of the University of Murcia. Investigators provided a detailed explanation of the protocol to participants, and those choosing to participate gave their informed consent. Each participant received a unique code based on their arrival order. Following this, an external researcher then assigned the participants to the different groups with the aim of having two similar groups based on sex, age, and IMC. The specific group assignments were not known to either the researchers or the participants.

Three weeks before the start of the study, a recruitment phase was carried out, in which potential participants were recruited and informed about the details of the study. From a total of 63 individuals initially recruited, fifty-eight volunteers completed the trial. Participants who abandoned the trial were for personal reasons unrelated to the study. Two visits were made during the experimental phase of the intervention: the initial and the final visit. At both visits, blood, faeces, and urine samples were obtained from participants, and anthropometric measurements were also taken. Two deliveries of 15 blister packs of 100g control or reformulated cooked meat product were made, at baseline and after 17 days. Individuals consumed one blister pack per day for 6 days per week. Throughout the trial, subjects recorded their complete diet in a collection notebook, which was given to the researchers at the end of the study.

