#### 1.2. Participants

The study comprised a total of 58 subjects divided into two groups of 29 individuals with similar characteristics (Table 2). To participate in the study, subjects were required to be between 18 and 65 years of age and body mass index (BMI) between 18.5 and 30 kg/m2. Participants also had to avoid all of the exclusion criteria: use of antibiotics in the last 3 months; use of medication for hypertension or for the treatment of hyperlipaemia; consumption of pre- or probiotic supplements; consumption of omega-3 or omega-6 supplements; eating , intestinal or similar problems; diabetes mellitus, chronic kidney disease, liver disease, infectious diseases or any type of cancer; having donated blood in the last month; having undergone surgery within the last three months; abusive alcohol consumption; being vegetarian; being pregnant; being a smoker; and participation in other clinical trials in the last 3 months.

		0 1	
	Control	Intervention	p-value 
Age (years)	$26.6 \pm 11.5$	$26.7 \pm 11.7$	0.97
Men	15	14	1.00
Women	14	15	1.00
BMI (kg/m2)	$23.7\pm2.7$	$23.6\pm2.8$	0.98
Weight (kg)	$66.6 \pm 11.8$	$68.4 \pm 12.7$	0.58
Fat mass (%)	$26.0\pm9.0$	$26.9\pm9.0$	0.71
Total colesterol (mg/dl)	$175.8 \pm 34.6$	$178.0 \pm 30.9$	0.80
Oxidized LDL (ng/mL)	$238.6 \pm 52.1$	$233.6 \pm 52.4$	0.71

Table 1. Distribution of volunteer demographics
---

 $^1$  p-values between control and intervention groups were examined using a one-way analysis of variance (Tukey's test). The results are shown as mean  $\pm$  SD (n=29).

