# 1.3. Study Analyses

## **1.3.1.** Anthropometric measurements

The anthropometric analysis of the participants followed the protocol of the International Society for the Advancement of Kinanthropometry (ISAK). The following measurements were taken with the corresponding equipment: height (213 measuring rod, Seca deutschland, Germany), weight (body fat monitor with scale BF400, OMRON Healthcare, Japan), body mass index (BMI) and percentage of fat mass (body fat monitor BF306, OMRON Healthcare, Japan). Abdomen circumference was also measured (201 antrophometric tape, Seca deutschland, Germany). In addition, hip and waist circumferences were measured to calculate the waist:hip ratio (WHR) (cm waist:cm hip), which is used to evaluate the development cardiovascular disease.

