#### 1.3.3.5. Bioinformatic analysis

For bacteria taxonomic assignment, ASVs were queried against the Silva database v.132 [The SILVA ribosomal RNA gene database project: improved data processing and web-based tools] using IDTAXA implemented in the R package DECIPHER. Sequences identified as non-bacterial were discarded.

The abundance matrix, the taxonomy assignment and the metadata obtained from each sample were merged and imported with the phyloseq v3.12 package. Alpha diversity was calculated in R using the phyloseq package, and several alpha indices were generated, such as ASV numbers, Chao1, ACE, Shannon, Simpson, InvSimpson, and Fisher and plotted using the function "plot richness". Beta diversity was calculated using weighted and unweighted Unifrac distances. To test for significant differences in community composition among different seasons, permutational multivariate analysis of variance using distance matrices (PERMANOVA) was conducted using the Adonis function in the R package, and the results were visualized by Principal Coordinates Analysis (PCoA).

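### The between-group test for continuous outcomes is an unadjusted change-score t-test in another form; adjusting for the baseline value already collected would be more precise unless the outcome is very stable

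*Protocol*

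**What the plan says.** Protocol section 1.4 states the aim of the between-group analysis as "To analyse the differences between groups in the evolution of the different variables". The method is that "an analysis of variance (ANOVA) was performed for repeated measures, with time (baseline and final) as the within-subject factor", with "the product consumed (Control and Intervention) as the between-subject factor". No baseline covariate or other adjustment appears in the model.

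Section 1.1 describes two visits, initial and final, and states: "At both visits, blood, faeces, and urine samples were obtained from participants". Anthropometry was also taken at both. So each of these outcomes has its own baseline value on file. The same section says that an external researcher "assigned the participants to the different groups with the aim of having two similar groups based on sex, age, and IMC" (IMC being BMI). Section 1.2 reports 29 participants per arm.

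**The concern.** The aim in section 1.4 corresponds to the product-by-time interaction. With only two times and two groups, that interaction is the same test as a t-test on final minus baseline. A change score fixes the slope of final on baseline at 1, whereas ANCOVA estimates it. If the true slope is well below 1, as with markers that vary within a person from week to week, the change score carries the noise of the baseline measurement into the comparison.

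The model also leaves out sex, age and BMI, on which the groups were deliberately made similar.

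What is at stake is precision, not bias or false positives. With 29 per arm, a real effect on a blood, stool or urine marker could be missed, or reported with a wider interval than the data require. The point covers only continuous outcomes with a value at both visits. It does not touch the PERMANOVA of beta diversity (section 1.3.3.5) or the chi-square tests of additive perception (section 1.4).

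**Working it through.** The protocol states no power, target difference or baseline-final correlation, so there is no design figure to reproduce.

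**Inputs**
- 29 per arm (section 1.2).
- Significance level 0.05 (section 1.4), taken as two-sided.
- Baseline SDs from Table 1: oxidised LDL 52.1 and 52.4 ng/mL, pooled √[(52.1² + 52.4²)/2] = 52.25; total cholesterol 34.6 and 30.9 mg/dl, pooled 32.8.
- Assumed: equal SD σ at both visits, and correlation ρ from 0.3 to 0.95.

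**1. Identity.** On one simulated data set with 29 per arm, the interaction F(1, 56) was 0.8765. The squared t on the change scores was also 0.8765, with the same p of 0.353.

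**2. Validity.** In 20,000 simulated trials per setting, the change-score test had a type I error of 4.8% to 5.1% for ρ from 0.3 to 0.98.

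**3. Variance per participant.** Change score: 2σ²(1 − ρ), 56 df. ANCOVA: σ²(1 − ρ²). The ratio of ANCOVA to change is (1 + ρ)/2.

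**4. Cost of the covariates.** With baseline value, sex, age and BMI, the residual df are 58 − 6 = 52. The ANCOVA variance is multiplied by 52/51 for chance imbalance in the baseline value. Sex, age and BMI are taken as balanced, as in Table 1 (men 15 v 14, age 26.6 v 26.7, BMI 23.7 v 23.6), and as explaining no further variance.

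**5. Worked case, oxidised LDL, ρ = 0.5.**
- SE of the change difference = 52.25 × √(2 × 0.5) × √(2/29) = 13.72. Detectable difference at 80% power = 2.851 × 13.72 = 39.1 ng/mL.
- SE under ANCOVA = 52.25 × √(0.75 × 52/51) × √(2/29) = 12.00. Detectable difference = 2.855 × 12.00 = 34.3 ng/mL.
- ANCOVA power for the 39.1 ng/mL difference: noncentrality 39.1/12.00 = 3.26 on 52 df, giving 89.2%.
- For total cholesterol, the same steps give 24.6 falling to 21.5 mg/dl.

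**6. Across the range** (four-covariate ANCOVA; the planned test has 80% power in every row)

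| ρ | (1 + ρ)/2 | ANCOVA power | 95% CI narrower by about | Detectable oxidised LDL difference, planned → ANCOVA (ng/mL) |
|---|---|---|---|---|
| 0.3 | 0.65 | 93.0% | 18% | 46.3 → 37.7 |
| 0.5 | 0.75 | 89.2% | 12% | 39.1 → 34.3 |
| 0.7 | 0.85 | 85.2% | 7% | 30.3 → 28.2 |
| 0.8 | 0.90 | 83.2% | 4% | 24.7 → 23.7 |
| 0.9 | 0.95 | 81.1% | 1% | 17.5 → 17.2 |
| 0.95 | 0.975 | 80.1% | 0% | 12.4 → 12.4 |

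Simulation of the full model (4,000 runs) gave 92, 90, 85, 84, 81 and 80%. The gain vanishes at ρ = 0.956 with four covariates, and at 0.962 with the baseline value alone.

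**7. Equivalent sample size.** Before the covariate cost, the planned test needs 29 × 2/(1 + ρ) per arm to match ANCOVA with 29: about 45 at ρ = 0.3, 39 at 0.5 and 34 at 0.7.

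**8. Chance baseline gaps.** A change score subtracts the whole gap and ANCOVA subtracts ρ times it, so they differ by (1 − ρ) × gap. For oxidised LDL the gap is 238.6 − 233.6 = 5.0: 3.5 ng/mL at ρ = 0.3 (3.5/16.2 = 0.22 SE) and 1.5 at ρ = 0.7 (1.5/10.6 = 0.14 SE). For cholesterol the gap is 178.0 − 175.8 = 2.2: 1.5 mg/dl (0.15 SE) and 0.7 (0.10 SE).

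**The case against.** The planned test is valid and answers the question that section 1.4 asks, so this is a better method set against an acceptable one. That is true, and it limits the severity. But the protocol does fix the between-group model, so the point is about a stated choice and not about detail left to a statistical analysis plan.

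The size is not known: ρ is assumed, and so is the 80% starting point. This stands as a limit on the claimed benefit. It is also a reason to estimate the slope, since the loss beyond break-even is very small (simulated power 78.7% against 78.9% at ρ = 0.98, baseline value only).

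Sex, age and BMI add nothing in the figures above: at ρ = 0.5 the baseline-only model has 89.3% power against 89.2%. This also stands. They are included because the allocation balanced on them, and the cost is negligible while that balance holds. Had they been left to chance imbalance, the factor would be 55/51, break-even would fall to about ρ = 0.85, and power at ρ = 0.9 would be 78.9%.

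The text reads as a finished trial, and a post hoc model should not quietly replace the documented one. This is fair, and it governs how the change is reported.

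Finally, validity rests on random allocation. Section 1.1 calls the trial randomised but describes groups being assigned so as to be similar. Both methods depend on this, so it does not favour either.

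**Conclusion.** The concern holds, as a matter of efficiency. The between-group test in section 1.4 is an unadjusted change-score comparison: valid, with correct type I error, but less precise than ANCOVA below a correlation of about 0.96. The gain is material where baseline and final values correlate weakly or moderately (about 13 power points at 0.3, 9 at 0.5, 5 at 0.7) and negligible at 0.9 or above. Blood, stool and urine markers may fall in the first group; weight, BMI and circumferences over 5 weeks may fall in the second. The documents do not say which outcomes would gain. Correcting chance baseline gaps is a minor extra, at most 0.22 standard errors for the two Table 1 markers examined.

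The figures assume random allocation, equal SDs at both visits, two-sided 0.05, and balance on sex, age and BMI as in Table 1. The change should be made, but the planned analysis is not invalid without it.

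**What to change.** In section 1.4, for continuous outcomes measured at both visits, make the between-group test an ANCOVA: final value on product, baseline value of the same outcome, sex, age and baseline BMI (entered once when BMI is the outcome). Report the adjusted difference with its 95% CI, and keep the repeated-measures ANOVA as a reported sensitivity analysis.

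Section 1.4 is in the past tense. If the data have already been analysed, say that the ANCOVA was added afterwards, label it post hoc, and report both results for every such outcome, so that neither is chosen by its result. Leave the PERMANOVA and chi-square analyses as they are.

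The cost is one or two sentences, a re-run in SPSS and four degrees of freedom (56 to 52).
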